### **8.3.3 Exploratory Endpoints**

- Pharmacokinetic endpoints from a population PK analysis
  - Absorption profile characterization, if it is supported by the data
  - Apparent clearance (CL/F)
  - Apparent volume of distribution (Vz/F)
  - $C_{trough}$  levels at Day 14 after first dose, at Weeks 4, 12, and 24 predose, and at Day 14 after dose at Week 24.

## 8.4 Analysis Sets

### 8.4.1 Enrolled

All participants who sign informed consent.

### 8.4.2 Intention-to-Treat

The Intention-to-Treat (ITT) Analysis Set will include all patients randomly allocated to a treatment, based on the intention to treat “as randomized” principle (ie, the planned treatment regimen rather than the actual treatment given in case of any difference). Patients will be analyzed according to their randomized treatment.

### 8.4.3 Per-Protocol

The Per-Protocol (PP) analysis set includes all randomized and treated patients (hence a subgroup of the ITT analysis set) who do not have any important clinical protocol deviations (67).

Patients will be analyzed according to their randomized and received treatment, as receipt of a different treatment from that assigned is an important protocol deviation.

The following are criteria for inclusion in the PP analysis set:

- Received the randomized treatment;
- Compliance with all entry criteria;
- Absence of important clinical trial protocol violations per regulatory definition;
- Adequate compliance with and sufficient exposure to IMP;

The criteria for the PP population will be defined in detail in the SAP; major protocol violators excluded from the PP analysis set will be identified.

Patients who achieve less than 20% improvement in both swollen and tender joint counts at Week 24 (non-responders) will be discontinued from the treatment. These patients will remain in the trial safety analysis set and participate in the safety and immunogenicity assessments.

### 8.4.4 Safety

The Safety Analysis Set will include all randomized patients who receive at least one dose of trial treatment. Patients will be analyzed according to the actual treatment they receive during the trial.

### 8.4.5 Population Pharmacokinetics

The Pharmacokinetic Analysis Set will include all patients who receive at least 1 dose of trial treatment and have at least 1 valid post-dose pharmacokinetic assessment without protocol deviations which could potentially affect PK.

## 8.5 Description of Statistical Analyses

### 8.5.1 General Considerations

Full details of all planned analyses will be provided in the SAP, to be finalized and approved prior to database lock.

Baseline is defined as the day on which the first dose of the IMP (blinded trial drug) is administered.

Descriptive statistics will be given with reference to the analysis set deemed appropriate for each particular endpoint.

The following descriptive statistics will be used to summarize the trial data per treatment group on the basis of their nature unless otherwise specified:

- Continuous variables: n (number of non-missing observations), mean, standard deviation, 95% confidence interval (CI), median, minimum, and maximum
- Categorical variables: Frequencies and percentages
- Time to event variables: Kaplan-Meier estimates and 95% CIs

No correction for multiplicity is anticipated.

### 8.5.2 Analysis of Primary Endpoint

The primary safety (safety population) endpoint will be summarized by treatment group using the Safety analysis set. Incidence of AESIs and 95% CIs will be provided for each treatment group. Half width of 95% CIs for the difference in incidence for the most commonly observed clinical events of AESI (hypersensitivity) will also be calculated.

### 8.5.3 Analysis of Secondary Endpoints

#### 8.5.3.1 Analysis of Key Secondary Efficacy Endpoint

The proportion of patients with an ACR20 response in both the treatment groups at Week 12 will be reported along with 95% CIs.

The analyses will be carried out on both the ITT and the PP analysis sets.

#### 8.5.3.2 Analysis of Other Secondary Efficacy Endpoints

Other secondary efficacy endpoints will be summarized descriptively according to the type of outcome.

The proportion of patients with ACR20, ACR50, and ACR70, DAS28 low disease activity and remission, and ACR/EULAR Boolean remission rates, will be reported along with 95% CIs.

Continuous outcomes (eg, DAS28, SDAI, and CDAI mean change from baseline) will be summarized using descriptive statistics.

The summaries will be presented on both the ITT and the PP analysis sets.

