### Exploratory Objective

The exploratory objective is to evaluate population pharmacokinetics (PK) on MSB11022-**CCI** and Humira® in patients with moderately to severely active RA.

**Methodology:** This trial is a two-arm, randomized, multicenter, double-blind, parallel group trial designed to compare the safety, immunogenicity, and efficacy of MSB11022-**CCI** with Humira® in approximately 260 randomized patients with moderately to severely active RA during a 52 week period.

Baseline is defined as the day on which the first dose of the investigational medicinal product (IMP) (blinded trial drug) is administered (Week 0). The trial will include a pre-trial evaluation period (screening period, from 28 days to 3 days prior to drug administration), a double-blind 48-week treatment period to evaluate long-term safety and immunogenicity, a 4-week safety follow-up visit, and a 4-month safety evaluation period. The primary safety endpoint will be assessed up to Week 52, key secondary efficacy endpoint will be assessed at Week 12. The analysis for the key secondary efficacy endpoint will be descriptive.

Re-screening will be allowed once for those patients who do not meet the inclusion/exclusion criteria within the above specified time limits. The Medical Monitor must promptly inform the Sponsor about requests and reasons for re-screening. An Independent Data Monitoring Committee (IDMC) will review the safety data from this trial on an ongoing basis.

Eligible patients will be randomized in permuted blocks in a 1:1 ratio by an interactive web response system (IWRS) to receive either MSB11022-**CCI** subcutaneous (s.c.) or Humira® s.c. at a dose of 40 mg every other week starting at baseline up to and including Week 48.

Randomization will be stratified by the type of systemic therapy previously received: non-biological (biologic naïve patients) versus biological (biologic experienced patients). Patients who previously received both (biological and non-biological systemic therapies) will be assigned to the “biological” group. The exposure to previous biological agents will be limited to one tumor necrosis factor (TNF) inhibitor other than adalimumab. The participation of patients in the previous biological systemic therapy stratum will be capped at 20% of the total number of patients randomized. Capping will be enforced through application of an IWRS.

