### 4.2.2 Other Secondary Objectives

Other secondary objectives are as follows:

- To evaluate the immunogenicity profile of MSB11022-CCI compared to Humira® in patients with moderately to severely active RA up to Week 52
- To further compare the efficacy and safety of MSB11022-CCI compared to Humira® in patients with moderately to severely active RA up to Week 52
- To compare quality of life (QoL) and physical function on MSB11022-CCI with Humira® in patients with moderately to severely active RA
- To compare injection site pain levels of MSB11022-CCI versus Humira®.

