15.2.2.3 ACR Component Variables

Summary statistics will be presented for the actual values for the ACR component variables (tender joint count (TJC), swollen joint count (SJC), Patient's and Physician's Global Assessment of Disease Activity, Patient's Assessment of Arthritis Pain – divided by 10, Patient's Assessment of Physical Function as measured by the HAQ-DI and CRP) and change from baseline values, by visit and treatment arm.

Line graphs will also be provided to display the change from baseline over time for the ACR component variables, by treatment arm.

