15.2.2.4 DAS28-ESR

The Disease Activity Score calculated on 28 joints (DAS28-ESR) is a composite score derived from four measures. Components of DAS28-ESR are:

- Number of tender joints (out of the 28)
- Number of swollen joints (out of the 28)
- Erythrocyte sedimentation rate (ESR)
- Patient's Global Assessment of Disease Activity.

For DAS28-ESR, the 28 joints to be examined and assessed as tender or not tender for TJC and to be examined and assessed as swollen or not swollen for SJC include 14 joints on each side of the subject's body: 2 shoulders, 2 elbows, 2 wrists, 10 metacarpophalangeal joints, 2 interphalangeal joints of the thumb, 8 proximal interphalangeal joints, and 2 knees.

DAS28 will be derived using the following formula:

$$DAS28 = 0.56*\sqrt{(TJC28)} + 0.28*\sqrt{(SJC28)} + 0.014*GH + 0.70*ln(ESR)$$

where:

- TJC28 = 28 joint count for tenderness
- SJC28 = 28 joint count for swelling
- ln(ESR) = natural logarithm of ESR

• GH = the general health component of the DAS (i.e., Patient's Global Assessment of Disease Activity, assessed using a scale of 1 to 100 where 100 is maximal activity; For analyses, GH will be divided by ten and converted to a 0.5 scale, i.e. 0, 0.5, 1, 1.5 etc. where [0-0.25] = 0, [0.25-0-75] = 0.5, [0.76-1.25] = 1, etc.).

A DAS28-ESR of > 5.1 implies active disease, < 3.2 low disease activity, and < 2.6 remission. A change of ≥ 1.2 (twice the measurement error) is defined as a significant change of the disease activity state.

The proportion of subjects with DAS28 low disease activity and remission at Weeks 2, 4, 8, 12, 24 and 52 will be reported along with Exact 95% CIs calculated with the Clopper-Pearson method.

Summary statistics will be presented for the actual DAS28-ESR values and change from baseline, by visit and treatment arm. Similarly for the DAS28-ESR component variables.

Line graphs will also be provided to display the change from baseline over time for DAS28-ESR and its component variables, by treatment arm.

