15.2.2.5 CDAI

The CDAI is a composite index (without acute-phase reactant) for assessing disease activity. CDAI is based on the simple summation of the swollen and tender joint counts based on 28 joints along with the Patient's and Physician's Global Assessment of Disease Activity (VAS) for estimating disease activity. The CDAI ranges from 0 to 76.

The CDAI is calculated based on the following formula:

$$CDAI = SJC28 + TJC28 + GH + PGA$$

where:

- TJC28 = 28 joint count for tenderness
- SJC28 = 28 joint count for swelling
- GH = the general health component of the DAS (i.e., Patient's Global Assessment of Disease Activity assessed using a scale of 1 to 100 where 100 is maximal activity; For analyses, GH will be divided by ten and converted to a 0.5 scale, i.e. 0, 0.5, 1, 1.5 etc. where [0-0.25] = 0, [0.25-0-75] = 0.5, [0.76-1.25] = 1, etc.)
- PGA = Physician's Global Assessment of Disease Activity assessed using a scale of 1 to 100 where 100 is maximal activity. For analyses, PGA will be divided by ten and converted to a 0.5 scale, i.e. 0, 0.5, 1, 1.5 etc. where [0-0.25] = 0, [0.25-0-75] = 0.5, [0.76-1.25] = 1, etc.

Summary statistics will be presented for the actual CDAI values and change from baseline, by visit and treatment arm, at Weeks 2, 4, 8, 12, 24 and 52.

Line graphs will also be provided to display the change from baseline over time for CDAI, by treatment arm.

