15.2.2.6 SDAI

The SDAI is the numerical sum of five outcome parameters: tender and swollen joint counts (based on a 28-joint assessment), Patient's and Physician's Global Assessment of Disease Activity (VAS) and level of CRP (mg/dL).

The SDAI is calculated based on the following formula:

$$SDAI = SJC28 + TJC28 + GH + PGA + CRP$$

where:

- TJC28 = 28 joint count for tenderness
- SJC28 = 28 joint count for swelling
- GH = the general health component of the DAS (i.e., Patient's Global Assessment of Disease Activity assessed using a scale of 1 to 100 where 100 is maximal activity; For analyses, GH will be divided by ten and converted to a 0.5 scale, i.e. 0, 0.5, 1, 1.5 etc. where [0-0.25] = 0, [0.25-0-75] = 0.5, [0.76-1.25] = 1, etc.)
- PGA = Physician's Global Assessment of Disease Activity assessed using a scale of 1 to 100 where 100 is maximal activity. For analyses, PGA will be divided by ten and converted to a 0.5 scale, i.e. 0, 0.5, 1, 1.5 etc. where [0-0.25] = 0, [0.25-0-75] = 0.5, [0.76-1.25] = 1, etc.
- CRP = C-reactive protein in mg/dL.

Summary statistics will be presented for the actual SDAI values and change from baseline, by visit and treatment arm, at Weeks 2, 4, 8, 12, 24, and 52.

Line graphs will also be provided to display the change from baseline over time for SDAI, by treatment arm.

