15.3 Other Secondary Endpoint Analyses

15.3.1 Quality of life

The three QoL questionnaires completed are the Health Assessment Questionnaire-Disability Index (HAQ-DI), the European Quality of Life – 5 Dimensions and 5 Levels (EQ-5D-5L) and the 36-item Short-Form Health Survey (SF-36).

A summary of QoL questionnaire completion, including reason for non-completion will be presented by visit and treatment arm.

Summary statistics for absolute value and absolute change from baseline will be presented for domains and/or total scores at baseline and at Weeks 12, 24, and 52 by treatment arm.

The summaries will be presented using both the ITT and the PP analysis sets.

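### DAS28-ESR, CDAI, SDAI and HAQ-DI are summarised by arm only, with no between-arm difference and no use of baseline value or prior-biologic stratum, although the objectives are to compare

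*Protocol*

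**What the plan says.** Protocol 8.5.3.2: "Continuous outcomes (eg, DAS28, SDAI, and CDAI mean change from baseline) will be summarized using descriptive statistics".

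The SAP carries this out endpoint by endpoint:
- DAS28-ESR (15.2.2.4): "Summary statistics will be presented for the actual DAS28-ESR values and change from baseline, by visit and treatment arm".
- CDAI (15.2.2.5): "Summary statistics will be presented for the actual CDAI values and change from baseline, by visit and treatment arm, at Weeks" 2 to 52.
- SDAI (15.2.2.6): "Summary statistics will be presented for the actual SDAI values and change from baseline, by visit and treatment arm, at Weeks" 2 to 52.
- HAQ-DI, with the other questionnaires (15.3.1): "Summary statistics for absolute value and absolute change from baseline will be presented for domains and/or total scores", at baseline and Weeks 12, 24 and 52.

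SAP 11.1 defines the content of these tables: n, number missing, mean, SD, quartiles, range and a 95% CI, shown for each arm. Line graphs of change over time are added for DAS28-ESR, CDAI and SDAI.

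Protocol 4.2.2 sets the purpose: "To further compare the efficacy and safety of" the two products up to Week 52, and to compare quality of life and physical function. On allocation, the Protocol Synopsis says: "Randomization will be stratified by the type of systemic therapy previously received". The biological stratum is capped at 20% of patients randomised.

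For the binary ACR endpoints the SAP goes further. Section 15.2.1 gives ACR20 at Week 12 a Newcombe 95% CI for the difference between arms. Sections 15.2.2.1 and 15.2.2.2 extend the same analysis to ACR20 at other visits and to ACR50 and ACR70.

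**The concern.** A comparison objective calls for an estimate of the difference and its uncertainty. For these four scores the plan stops at two separate columns. Two by-arm CIs placed side by side are not a CI for the difference.

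Raw change from baseline is also not adjustment for baseline. A chance imbalance in the baseline score carries into the difference in mean change. The baseline scores and the prior-biologic stratum are both collected, and SAP 10.2.2 even has a rule for correcting a wrong stratum value, but no planned analysis of these endpoints uses either as a covariate. SAP 15.2.2 also rules out subgroup breakdowns for efficacy endpoints other than ACR20 and ACR50.

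At stake is how clearly the supportive efficacy evidence can be read, and whether the between-arm estimate is fixed in advance or worked out afterwards by whoever needs it.

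**Working it through.** **1. The plan's own precision figure.** Protocol 8.1 and SAP 7.1 state a precision of 12.0% at an incidence of 26.0%, and 9.0% at 11.0%. Take this as the half-width of a 95% CI for a difference between two arms of 100.
- Simple (Wald) formula, 1.96 × √(2p(1−p)/n): 1.96 × √(2 × 0.26 × 0.74/100) = 12.16 points; 1.96 × √(2 × 0.11 × 0.89/100) = 8.67 points.
- Newcombe: 12.06 and 8.99 points, which matches.
- A single-arm CI at n = 100 gives 8.60 and 6.13, and 130 per arm gives 10.66 and 7.61 (Wald). Neither fits.

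So the trial is sized on the precision of a between-arm difference. No such quantity is specified for the continuous efficacy scores.

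**2. Unadjusted precision available for DAS28-ESR.** Half-width = 1.96 × SD × √(2/n). At 100 per arm this is 0.277 × SD. The documents give no SD of change. For an assumed 1.0, 1.2 or 1.5 it is 0.28, 0.33 or 0.42 units. Protocol 5.2.3.3 says a change of 0.6 may already be clinically meaningful. That is a yardstick for change in response to therapy, not a between-arm margin, but it shows that the estimate would be informative at the planned size.

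**3. Gain from baseline adjustment.** Let r be the baseline-to-visit correlation and k the ratio of follow-up SD to baseline SD. Per patient, in units of the baseline variance:
- variance of raw change: 1 + k² − 2rk
- residual variance after adjustment: k²(1 − r²)
- ratio: k²(1 − r²)/(1 + k² − 2rk), which equals (1 + r)/2 when k = 1

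| r | k | Variance ratio | CI width ratio (square root) | Narrower by |
|---|---|---|---|---|
| 0.3 | 1 | 0.65 | 0.81 | 19% |
| 0.5 | 1 | 0.75 | 0.87 | 13% |
| 0.7 | 1 | 0.85 | 0.92 | 8% |
| 0.3 | 1.3 | 1.69 × 0.91/1.91 = 0.805 | 0.897 | 10% |
| 0.5 | 1.3 | 1.69 × 0.75/1.39 = 0.912 | 0.955 | 4.5% |
| 0.7 | 1.3 | 1.69 × 0.51/0.87 = 0.991 | 0.995 | 0.5% |

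Both r and k are assumptions. A k above 1 is plausible because the entry criteria (Protocol 5.3.1) require at least 6 swollen and 6 tender joints, which cuts off the lower end of the baseline distribution.

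With an SD of change of 1.2 at 100 per arm, the half-width of 0.33 becomes 0.27, 0.29 or 0.31 for k = 1. For k = 1.3 it becomes 0.333 × 0.897 = 0.30, 0.333 × 0.955 = 0.32 or 0.333 × 0.995 = 0.33.

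**4. Chance imbalance.** If the arms differ by d at baseline, the difference in mean change is shifted by (rk − 1)d. For r = 0.3, 0.5, 0.7 this is −0.7d, −0.5d, −0.3d at k = 1, and −0.61d, −0.35d, −0.09d at k = 1.3. Adjustment for baseline removes it.

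**5. What can be recovered.** From n, mean and SD per arm, an unadjusted difference and its CI follow by arithmetic. The adjusted difference needs the within-patient relation of baseline to follow-up and the stratum membership, which the tables do not show.

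**The case against.** The trial is openly descriptive. Safety is the primary objective, there is no efficacy margin, and SAP 11.2 treats all other endpoints as supportive. Protocol 3.1 gives the efficacy-equivalence role to a separate Phase III psoriasis trial of the citrate formulation. The SAP's own list of objectives also omits the protocol's aim of further comparing efficacy up to Week 52, although it keeps the Week 12 efficacy and the quality-of-life and physical-function comparisons. Baseline scores are tabulated by arm (SAP 12.4), so an imbalance would be seen, and stratified blocks already balance prior biologic use. All of this stands, and it limits the weight of the point. It does not remove it: the ACR endpoints show that, in this same descriptive trial, a difference with a CI is reported without any test.

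Some stronger readings are tempting, but the documents do not support them.
- A reader might infer that the scores come with no measure of uncertainty. SAP 11.1 gives each arm's mean an SD and a 95% CI.
- A reader might infer that the ACR20 difference is adjusted and these scores were singled out. The Newcombe interval there is unadjusted too. ACR20 is a precedent for reporting a difference, not for adjusting it.
- A reader might regard these scores as the most sensitive efficacy measures. Protocol 5.2.3.3 calls SDAI sensitive, but comparable with DAS28 and the ACR criteria.
- A reader might turn the gain into a smaller trial. The size rests on AESI precision and 200 patients at Week 52, so that does not follow.

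One objection bears on the remedy. Week 24 non-responders stop IMP and stay for safety and immunogenicity assessments (Protocol 5.2), so any Week 52 estimate rests on a missing-data assumption that must be stated.

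**Conclusion.** The point holds as a gap between objective and analysis. For DAS28-ESR, CDAI, SDAI and HAQ-DI the plan gives no between-arm difference with a CI, and uses neither baseline value nor stratum. That finding needs no assumption.

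The size of the gain does need assumptions. The CI would be about 8% to 19% narrower for r between 0.7 and 0.3 with equal variances, and about 0.5% to 10% narrower if the follow-up SD is 1.3 times the baseline SD. The documents give neither r, nor k, nor an SD. The gain from the stratum term cannot be quantified from them either. The firmer benefits are a pre-specified estimate and the removal of chance baseline imbalance.

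This is a supportive addition. It is not an invalid analysis or a sample-size error, and it does not affect the AESI result or ACR20 at Week 12.

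**What to change.** Keep every descriptive table. Add to SAP 15.2.2.4 to 15.2.2.6 and 15.3.1 an ANCOVA at each of Weeks 12, 24 and 52 for DAS28-ESR, CDAI, SDAI and HAQ-DI, with arm, baseline value and prior-biologic stratum (the corrected value under SAP 10.2.2). Report the adjusted mean difference with its 95% CI, on the ITT and PP sets as already planned, with no test and no margin.

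State the missing-data assumption, above all for Week 52, and say how scores after IMP discontinuation are treated. Protocol 8.7 promises missing-data handling for all secondary endpoints. SAP 11.4.1 covers ACR20 at Week 12, and beyond the HAQ-DI scoring rules in 15.3.1.2 there is no rule for these scores.

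Make the change before database lock and unblinding. If that point has passed, label the results as unplanned, as SAP section 5 requires. The cost is some SAP text, including the missing-data statement, and a few outputs. No new data are needed.

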### 8.5.3.3 Analysis of Safety Endpoints

Safety endpoints below will be summarized by treatment group:

- Treatment-emergent AEs, SAEs, AESIs, and deaths
- Clinical laboratory values including hematology, chemistry, and urinalysis
- Vital signs
- Physical exam
- 12-lead ECG

Adverse events will be coded with the latest version of the Medical Dictionary for Regulatory Activities and summarized by treatment group overall, by severity, and by relationship to MSB11022-CCI [REDACTED] or Humira®.

The nature, severity and frequency of the adverse drug reactions in patients who received MSB11022-CCI [REDACTED] will be compared with those who receive Humira® to evaluate comparability of safety.

AEs and concomitant medications will be recorded at each visit: screening, baseline (Week 0), and Weeks 2, 4, 8, 12, 24, 36, 48, and 52.

Summary statistics will be used to present changes from baseline in continuous laboratory and vital sign variables.

Shift tables will be used to present changes in categorical laboratory variables.

All clinical laboratory data will be stored in the database in the units in which they were reported and using the laboratory reference ranges. Patient listings and summary statistics at each assessment time will be presented using the International System of Units (SI units). Laboratory data not reported in SI units will be converted to SI units before processing.

Safety endpoints will be analyzed using the safety analysis set.

